5.5 Rationale for this study

To date NT-814 has been tested in 90 volunteers in 4 phase 1 studies of which 15 subjects were dosed with 200 mg up to 29 days. To date only 1 female subject has been dosed. The aim of this study is to investigate the PK and safety of NT-814 in post-menopausal women with hot flashes to help inform design of subsequent studies in the target population. The target population of post-menopausal women is required to have a minimum hot flash frequency and severity requirement for entry into this study. These characteristics have been selected as it is deemed to be important to define the safety profile of NT-814 in a controlled setting in a population with similar characteristics to that to be studied in further development due to the nature of the symptoms associated with the disease under study: hot flashes are often associated with symptoms such as palpitations, tachycardias and dizziness. To help in this assessment a careful pre-dose characterization of the subjects will be carried out on before dosing on Day -1, the study will be placebo controlled and involve 24-hour ECG monitoring through the first 7 days of dosing, when steady state plasma drug levels are predicted to be reached.

This study will be conducted in compliance with the protocol, Good Clinical Practice (GCP), the Declaration of Helsinki (with amendments), and in accordance with local legal and regulatory requirements.

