7.4 Withdrawal criteria

A subject should be withdrawn from treatment if they meet the discontinuation criteria in Section 9.8. If a subject is discontinued at any time after entering the study the investigator will make every effort to see the subject and complete the early termination visit assessments.

Subjects may withdraw from the study at any time without stating a reason and without prejudice to further treatment. The Investigator may withdraw a subject from the study and discontinue study treatment and assessments at any time.

Early discontinuation of any subject who has given informed consent to participate will be recorded including the reason for discontinuation. The primary reason for a subject withdrawing prematurely will be selected from the following standard categories of early discontinuations:

- **Failed to meet randomization criteria**
- **Adverse Event (Adverse Reaction):** Clinical events occurred or laboratory results are reported that in the medical judgment of the investigator are grounds for discontinuation in the best interests of the subject.
- **Withdrawal of Consent:** The subject desired to withdraw from further participation in the study. The subject is not obliged to provide any reason for withdrawal of consent, but where a reason is given this will be recorded on the eCRF.
- **Protocol Violation:** The subject failed to adhere to the protocol requirements, at the investigator's discretion e.g. the subject needs to start taking a medication from the prohibited medications list (Section 9.13.2).

- **Lost to Follow-Up:** The subject stopped coming for visits and study personnel were unable to contact the subject.
- **Other:** The subject was terminated for a reason other than those listed above, such as theft or loss of study drugs or electronic equipment or termination of study by Sponsor.

All subjects who withdraw from the study may be replaced.

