Eligible subjects will be admitted to a Phase 1 Unit as an inpatient on the morning of Day -1 and will be fitted with and instructed on use of a sternal skin conductance monitor and Holter monitor which will be worn continuously until discharge from the clinic on Day 8; both the Holter monitor and sternal skin conductance monitor will be refitted on return to the Phase 1 Unit on Day 14. Routine safety monitoring will be carried out in a manner that will form the baseline for comparisons for the remainder of the study.

On Day 1, the subjects will be randomized in a 3:1 ratio to once daily (morning) doses of NT-814 or placebo, to be taken for a total of 14 days. Subjects will be monitored as an inpatient from Day -1 to Day 8 and will undergo blood draws for intensive PK sampling, safety monitoring and for impact on blood hormonal profiling as well as 24-hour skin conductance measurements and continuous completion of hot flash diaries.

Subjects will be discharged from the clinic on Day 8 without any monitoring devices, providing there are no safety concerns and will undergo dosing for a further 5 days as an outpatient. Subjects will be instructed to continue recording details of the hot flashes experienced, using the twice daily diary. They will be provided with the continuous daily diary and instructed to start completing this upon waking on the morning of Day 14 prior to admission to the clinic. They will be re-admitted to clinic on the morning of Day 14 for the final dose and undergo the same assessments with the same devices including Holter and skin conductance as Day 1. Subjects will be discharged following the 24-hour post Day 14 assessments (Day 15). Subjects will return to the clinic, as outpatients, for a single PK sample on the mornings of Days 16 and 17 (48 hours and 72 hours after the Day 14 dose respectively).

Throughout the study, subjects will be closely monitored for safety including assessments of AEs, 12-lead ECGs, atrial oxygen saturation using pulse oximetry, vital signs (sitting and standing BP, heart rate, oral body temperature, and respiration rate), clinical labs and physical examinations.

At the end of each Cohort a blinded review of PK and safety data from all subjects will be conducted by the Safety Review Committee (see Section 10.7) to confirm that it is safe to proceed to the next

dose. This review must comprise complete data up to Day 17 from a minimum of 14 subjects per cohort.

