As outlined in the IB, the non-clinical data for sex differences in PK measures are not clear and are contradictory. Allowing for a step wise dose escalation with adequate monitoring and PK based stopping limits is considered an appropriate means of conducting the study to allow for a comparison of PK across sexes and providing for the maximum chance of achieving full target engagement.

The C_{max} pharmacokinetic safety margin is based on the no-observed-adverse-effect-level (NOAEL) in the rat 3-month toxicity study. In this study GSK1144814A (vehicle, 5, 25 or 100 mg/kg/day) was given orally to rats for 13 weeks. There were no adverse, test-article related changes; therefore, the NOAEL was considered to be 100 mg/kg/day and corresponded to a geometric mean AUC of 95900 ng.h/mL and a geometric mean C_{max} of 6500 ng/mL. The use of rat data to determine C_{max} stopping criteria is felt to be acceptable as dose limiting toxicology in the most sensitive species (monkey) was related to total exposure (AUC) and not related to C_{max}, and there have been no adverse events (AEs) of concern related to C_{max} in the four Phase 1 clinical studies conducted thus far.

The study starting dose of 50 mg is anticipated to provide safety margins of approximately 12- and 14-fold respectively for AUC₀₋₂₄ and C_{max}. Subjects will be dosed and monitored in a controlled Phase 1 Unit clinic setting for the first 8 days of dosing and will only be escalated to the next cohort only when safety and PK data have been analyzed.

The target exposure of 14040 ng.h/mL (geometric mean AUC_{0-24} achieved with 200 mg daily dose in males for 28 days) gives a safety margin of approximately 3-fold against the 41900 ng.h/mL observed value while the predicted geometric mean C_{max} of 1836 ng/mL (at the 200 mg daily dose and after 14 days' administration) gives a safety margin of ~3.5 fold against the C_{max} .

No dose will be given that is expected to exceed a geometric mean AUC_{0-24} of 20950 ng.h/mL (2-fold safety margin).

As detailed in Section 10.7, the Safety Review Committee will evaluate safety and tolerability data from each cohort prior to escalating to the subsequent dose.

If study stopping criteria (see Section 9.9) have not been met and there are no concerning safety signals, the subsequent Cohort will proceed to the next dose.

If study stopping criteria are met, no further subjects will be dosed and the study will be terminated.

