9.8 Discontinuation criteria

Subjects meeting any of the following criteria (regardless of treatment assignment) will be required to stop study medication and complete the early termination visit assessments:

- Intolerable complaints of undesirable sexual side effects from the study medication
- Oxygen saturation < 90% during a laboratory session that does not increase after administration of supplemental oxygen.
- If AST and ALT increase to ≥ 3 times the upper limit of normal
- Clinically relevant cardiovascular AE such as ventricular tachycardia or atrial fibrillation

- Signs of dehydration (e.g. orthostatic hypotension or decreasing urine outflow, impaired renal function or biochemistry profile change from the baseline, weight loss more than 10% from the baseline)

Subjects that discontinue early may be replaced.

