9.9 Cohort and dose escalation stopping criteria

After each cohort a Safety Review Committee will review and assess all the available safety and PK study data from all of the cohorts to date in order to make a decision on the dose for the next cohort of subjects.

Data from a minimum of 14 subjects from the previous cohort must be reviewed before a decision to escalate can be taken.

The stopping criteria listed below apply to stopping during a cohort or at the end of a cohort during safety data review. Events that occur during the cohort will be passed onto the unblinded safety reviewers who will inform the study team of whether stopping criteria have been fulfilled and in such a case no other subjects will be enrolled. Subjects on treatment will be asked to stop dosing and if possible go through the early termination assessments.

1. One subject who has received NT-814 reports a serious adverse event which is considered at least possibly related to the NT-814
2. Two or more subjects, who have received NT-814, have QTc prolongation, defined as QTc > 500 ms for both Bazett and Fridericia corrections, or a prolongation from baseline of > 60 ms, confirmed (persistent for at least 5 min) during continuous ECG monitoring deemed to be at least possibly related to study drug (discovered at the end of the cohort during safety data review or on repeat ECGs taken during the study at the pre-determined time points or at the time of an AE)
3. Two or more subjects, who have received NT-814, have tachycardia, defined as resting supine heart rate > 125 beats per minute persisting for at least 10 minutes deemed to be unrelated to a hot flash episode and at least possibly related to study drug during continuous ECG monitoring (discovered at the end of the cohort during safety data review or on a repeat ECGs taken during the study at the pre-determined time points or at the time of an AE)
4. Two or more subjects, who have received NT-814, have symptomatic bradycardia, defined as resting supine heart rate < 45 beats per minute or asymptomatic bradycardia defined as resting supine heart rate < 30 beats per minute while awake persisting for at least 10 minutes during continuous ECG monitoring deemed to be at least possibly related to study drug (discovered at the end of the cohort during safety data review or on a repeat ECGs taken during the study at the pre-determined time points or at the time of an AE)

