- 4 On Days 1 and 14, 12-lead ECG pre-dose and at 0.5, 1, 1.5, 2.0, 2.5, 3.0, 4.0, 8.0, 12.0 and 24.0 hours (all +/- 15 mins). The same assessments schedule is required on Day -1, starting at a similar time to that planned for Days 1 and 14. Once daily ECG recordings will be made just prior to dosing (approx. 30 mins) on all other days (Days 3-8) during inpatient stays.
- 5 Subjects need to complete paper-diary for the 2 weeks prior to Baseline visit to ascertain eligibility. Subjects also to record number of times awoken during the night due to flashes (Night time awakening (NTA). On Days -1 to 7 and on Day 14 subjects to record the occurrence and severity of the flash (scale 1 to 3) in a continuous diary. Diary to be provided to subjects during screening and at discharge on Day 8 and subjects instructed to start completing it after waking on the mornings of Day -1 and 14 prior to admission and throughout the day and night. In the inpatient treatment part of the study, subjects also push a button on the skin conductance monitor when they sense a hot flash
- 6 Skin conductance and Holter monitors to be fitted on Day -1 (24 hours prior to the planned study drug administration on Day 1) and remain in place until after the 24 hour assessments are completed on Day 8 and then for 24-hours from pre-dose on Day 14 to discharge on Day 15.
- 7 Study drug will be administered in the morning from Day 1 to Day 14. Study medication will be dispensed to the subject on Day 8 for self-administration at home (for Days 9 to 13).
- 8 LH sampling every 60 mins from time 0 (pre-dose on Day 1 and Day 7) to 8 hrs. The same sampling schedule is required on Day -1, starting at a similar time to that planned for Days 1 and 7.
- 9 PK Sampling at Pre-dose; 0.5; 1.0; 1.5; 2.0; 2.5; 3.0; 4.0; 5.0; 6.0; 8.0; 12.0; 24.0 hours; 48.0, 72.0 hours after Day 14 only.
- 10 Pre-dose samples for PK and LH to be taken within 30 minutes prior to dose administration
- 11 Telephone follow up visit, unless deemed by the investigator that a clinic visit is more appropriate to follow up an adverse event
- 12 Where possible, all subjects who are withdrawn or withdraw from the study early will undergo the Early Termination Visit assessments.

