10.4.2 Physical examinations

A full physical examination will be conducted at the time points indicated in the Study Schedule in [Table 2](#). This will be completed by a physician or an appropriate qualified delegate.

A full physical examination is composed of a review of the following body systems:

- General appearance
- Skin
- Head, eyes, ears, nose and throat
- Respiratory
- Cardiovascular
- Abdomen (including liver and kidneys)
- Musculoskeletal
- Neurological

Any abnormalities that are identified at the Screening Visit will be documented on the medical history eCRF page. Any changes (including new and worsening findings) between the Screening Visit and final study visit should be captured as AEs on the AE eCRF page, as determined by the Investigator and documented in the subject's notes.

If an improvement/resolution of a physical examination finding documented in the subject's medical history occurs during the study, it should be recorded in the source document. If there is resolution of a physical examination finding previously noted as an AE, then the event resolution and stop date should be recorded on the AE eCRF page and documented in the subject's notes.

10.4.3 24-hour Holter monitoring

Subjects will be fitted with Holter monitors upon admission to the Phase 1 unit on Day -1. These will remain in place until after the 24-hour assessments are completed on Day 7 (Day 8). Subjects will be fitted with Holter monitors again upon admission to the clinic on Day 14. These will remain in place until after the 24-hour assessments are completed on Day 14 (Day 15).

10.4.4 12-lead ECGs

12-lead ECG data captured by the Holter monitors will be collected at the timepoints indicated in the Study Schedule in [Table 2](#).

On Days 1 and 14, resting 12-lead ECG data will be collected at the following timepoints: pre-dose and at 0.5, 1.0, 1.5, 2.0, 2.5, 3.0, 4.0, 8.0, 12.0 and 24.0 hours (all +/- 15 mins).

The same assessment schedule is also required on Day -1, starting at a similar time to that planned for Days 1 and 14. On Day 1 the 24 hour ECG must be performed prior to the dose of study medication the following morning.

Once daily ECG recordings will be made just prior to dosing (approx. 30 mins) on all other days during the inpatient stay (Days 3 to 8).

These specific 12-lead ECG recordings should be collected in accordance with the priority order of study assessments detailed in [Section 10.5](#).

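### The early termination visit schedules no 12-lead ECG or Holter, so a woman who stops during home dosing (Days 9-13) has no scheduled tracing or QTc reading after Day 8

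*Protocol*

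**What the plan says.** **Who attends.** Note 12 to Table 2 (protocol section 10): "Where possible, all subjects who are withdrawn or withdraw from the study early will undergo the Early Termination Visit assessments". Section 7.4 adds that after discontinuation "the investigator will make every effort to see the subject and complete the early termination visit assessments". Section 9.8 sends women there who meet a discontinuation criterion, one of which is "Clinically relevant cardiovascular AE such as ventricular tachycardia or atrial fibrillation". Section 9.9 does the same when a stopping criterion is met, QTc prolongation being one: "Subjects on treatment will be asked to stop dosing and if possible go through the early termination assessments".

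**What the visit contains.** The early termination column of Table 2 is marked for physical examination, outpatient visit, vital signs, AE/SAE recording, biochemistry/hematology and urinalysis. It is blank for 12-lead ECG and for Holter.

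**When ECGs are scheduled.** Protocol 10.4.4: "12-lead ECG data captured by the Holter monitors will be collected at the timepoints indicated in the Study Schedule". Note 4, section 10.4.4 and SAP 4.10.5 give serial recordings on Days -1, 1 and 14 and one pre-dose recording a day on Days 3 to 8. Table 2 also marks Screening. None of these places names early termination.

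**What happens after Day 8.** Section 8.4: "Subjects will be discharged from the clinic on Day 8 without any monitoring devices". Doses on Days 9 to 13 are taken at home. The Day 21 contact is normally a phone call.

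**The concern.** ECG change is a named safety endpoint, and several cohort stopping criteria in section 9.9 rest on the ECG: QTc, tachycardia, bradycardia, and ventricular tachycardia or atrial fibrillation. For liver injury, dehydration, hypotension and oxygen saturation, the early termination visit has a matching measurement. For QTc and rhythm it has only a heart rate and a cardiovascular examination, and neither yields a QTc value or a tracing. The protocol gives no reason for the difference.

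The woman most exposed to this is one without symptoms who stops while dosing at home. If a cohort stops for QTc, those still dosing at home are called to a visit whose schedule does not ask whether their own QTc is normal or has recovered. A woman with symptoms is better served, because section 9.9 foresees ECGs at the time of an AE.

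**Working it through.** The documents state no figure on this point, so there is none to reproduce. The check is a reading of the schedule followed by a count.

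**1. Is the blank cell real?** The 12-lead row of Table 2 has 11 visit cells: Screening and Days -1, 1, 7, 8 and 14 are marked, and early termination is not. The Holter row is marked on Days -1, 1, 7, 8, 14 and 15, and again not at early termination. Note 4, protocol 10.4.4 and SAP 4.10.5 agree with the table. By contrast, SAP 4.10.2 does name early termination for chemistry and hematology. The blank is therefore unlikely to be a fault of the text extraction.

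**2. Scheduled 12-lead readings after the first dose.** The serial schedule is pre-dose plus 0.5, 1, 1.5, 2, 2.5, 3, 4, 8, 12 and 24 h, which is 1 + 10 readings.

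| Source | Completer | Stops on Days 9-13 |
|---|---|---|
| After the Day 1 dose (24 h reading falls on Day 2) | 10 | 10 |
| Days 3-8, once daily | 6 | 6 |
| Day 14, pre-dose plus 10 | 11 | 0 |
| **Total** | **27** | **16** |

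One ECG at early termination gives 16 + 1 = 17. As a share of a completer's readings, that is 16/27 = 59% before and 17/27 = 63% after. It is the only reading of the 17 taken after dosing has ended.

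**3. Age of the last scheduled ECG at the last dose.** The last reading is about 30 minutes before the Day 8 dose. For a last dose on Day d, the age is d - 8 days and the number of doses since the reading is d - 7.

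- Stops on Day 9 before dosing, so the last dose was in clinic on Day 8: age 0 days, 1 dose since.
- Last dose on Day 9: age 1 day, 2 doses since.
- Last dose on Day 13: age 5 days, 6 doses since.

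The range is 0 to 5 days. Holter ends by discharge on Day 8, so it may run slightly past the last 12-lead reading but not into home dosing.

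**4. The same gap in a completer.** She also has no scheduled ECG between Day 8 pre-dose and Day 14 pre-dose, which is 14 - 8 = 6 days. Hers is closed by the Day 14 profile. The early stopper's is not closed at all.

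**The case against.** The best case for leaving the plan alone is that the consequence is small.

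- **Exposure.** Section 5.5 plans "24-hour ECG monitoring through the first 7 days of dosing, when steady state plasma drug levels are predicted to be reached", so home dosing is expected to be time without a reading, not a period of rising exposure. This stands, though it is a prediction, and section 5.4 reports only one woman among the 90 volunteers exposed before.
- **Nothing forbids an ECG.** The investigator can record one at the visit. SAP 8.1 would list it as unscheduled and leave it out of the summaries. This stands: what the plan lacks is a requirement and a place in the summary tables, not permission.
- **Yield.** The visit has no fixed time, follows the end of dosing and has no PK sample. One reading there says nothing about peak exposure. This also stands.
- **Other safeguards.** Under section 10.7 the Safety Review Committee may add assessments for later cohorts, the Day 21 call can become a clinic visit for ongoing AEs, and withdrawn women may be replaced. None of these gives a tracing to a woman without symptoms in the current cohort.

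A reader might infer more than the documents support:

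- **That women stopped for ventricular tachycardia or atrial fibrillation go untraced.** Such a diagnosis would usually already rest on a tracing.
- **That the empty cell costs each early stopper 11 readings.** Those 11 are the Day 14 serial profile, which no early termination visit would restore.
- **That dose escalation is put at risk.** Section 9.2 says: "If study stopping criteria are met, no further subjects will be dosed and the study will be terminated". The cohort-stop case can therefore arise at most once, with no later escalation to inform.

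**Conclusion.** The omission is real and consistent across the protocol and the SAP. A woman who stops on Days 9-13 has no scheduled ECG tracing or QTc reading after Day 8, and her last scheduled 12-lead ECG is 0 to 5 days old at her last dose. The remedy is worth one post-treatment reading per early stopper who attends (16 to 17). It can show a persistent abnormality or recovery, chiefly in women without symptoms.

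This is a cheap improvement to subject safety, not a flaw in an endpoint or a decision rule. The exposure-response model in SAP 8.11.7 needs QTcF paired with a concentration at the same timepoint, so it is unaffected. The documents do not say how many women would stop during home dosing; that the number is small is an assumption. The benefit also assumes that the woman attends, since the visit is held only where possible.

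**What to change.** 1. **Protocol Table 2:** mark a resting stand-alone 12-lead ECG in the early termination column, done first in line with the priority order in section 10.5.
2. **Protocol 10.4.4 and SAP 4.10.5:** name the early termination ECG, and say that it is not taken from a Holter.
3. **SAP 8.11.5:** state that it counts as a scheduled assessment, that its baseline is the last reading before dosing on Day 1 (the rule already used for Days 3 to 8), and that it is identified in outputs as stand-alone and not time-matched.

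Leave SAP 8.11.7 and the stopping criteria as they are. No Holter is needed at this visit.

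**Cost.** One table cell, a few sentences in a small amendment, and a few minutes (assumed about 10) per early stopper at a visit already planned. The sites already record a non-Holter ECG at Screening, since Holters are first fitted on Day -1.

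**Downside.** The change from baseline sets a stand-alone reading at an arbitrary hour against a Holter-derived pre-dose reading. It is a coarse check and must not be read as QTc at peak exposure.
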